General inclusion & exclusion criteria: Participants must be 21-55 years of age, able to read English and complete study surveys, report liking beer and consuming it at least once in the past 30 days, and report having consumed at least two alcoholic drinks on at least one day during the past 30 days (i.e., current drinkers). Participants will be excluded if their urine drug test indicates recent use of illegal drugs (except cannabis) and pregnancy for women. In addition women who report engaging in sexual activity with opposite sex partners without use of reliable birth control will be excluded. Participants will also be excluded for any of the following conditions: a history of medically-assisted detoxification; present with signs of current alcohol withdrawal; currently meet the severe threshold for alcohol use disorder according to DSM-5 (i.e., 6 criteria or more); currently meet DSM-5 substance use disorder criteria at any level (i.e., 2 or more criteria) for any substance besides alcohol; are currently seeking treatment for problem substance use; have engaged in intensive outpatient or inpatient treatment for substance use in the past 12 months; meet criteria for severe depression or have any serious psychological or medical history that contraindicates alcohol consumption; currently taking any medication that contraindicates alcohol use at the levels included in this study; and have BMI under 18.5 or over 35. Given that video recording is a critical aspect of the study, participants will be required to agree to video recording in order to take part in the study. Undergraduates enrolled at the University of Florida will be excluded from participating. Graduate and non-matriculating students will be allowed to participate as long as they are not enrolled in the College of Health and Human Performance.

Subgroup division: Participants will be further divided by drinking status (social vs. heavy drinkers) and mental health status (elevated vs. non-elevated depressed mood). This creates four combinations of subgroup category (2×2). Efforts will be made to recruit equal numbers of men and women in each of the 4 categories.

Sample size: As a pilot study, we will target enrollment of up to 40 participants (~10 in each subcategory as defined in the previous section).

Procedure

Pre-screening by phone:

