- a. *Drinking behaviors:* Past 30-day drinking behaviors and DSM-5 criteria for alcohol use disorder will be used as the basis for distinguishing social and heavy drinkers. The social drinker group will be those who (1) consume at least 1 but no more than 5 standard alcoholic drinks per week and (2) engage in infrequent binge drinking (i.e., 5 or fewer times per year, but allowing for 1 past interval of a maximum of 6 months' duration of up to twice weekly binge drinking). The heavy drinker group will be those who (1) consume at least 10 alcoholic drinks per week ; (2) engage in regular binge drinking (i.e., consume 5 or more drinks on one occasion or ≥ 4 for women 1 to 5 times on average per week); and (3) meet DSM-5 criteria for mild or moderate alcohol use disorder. These criteria are based on criteria outlined by King et al.¹⁹ The timeline followback (TLFB) interview will be used to obtain self-reports of drinking behavior with a focus on past-30-day behavior, however the extent to which recent drinking behavior resembles past-12-month and lifetime drinking behavior will be queried in order to make sure participants meet criteria for

one of these two categories. Those who drink but who did not clearly fall into one of these two groups will be excluded from participation.

- b. *Depression:* Patient Health Questionnaire (PHQ-2 and PHQ-9) will be used for depression screening. The non-elevated depressed mood group will be those who scored less than 3 on PHQ-2 (i.e., negative PHQ-2). Elevated depressed mood group will be those who scored 3 or more on the PHQ-2 (i.e., positive PHQ-2) and 5 or more on the follow-up PHQ-9. Those who scored 20 or more (i.e., severe depression) will be excluded from the study and offered local referral options for treatment.

Once the participants pass the breath alcohol and urine testing, and meet all the eligibility criteria, they will be scheduled for the first of two alcohol drinking sessions. Compensation for the in-person screening appointment will be \$10 for those deemed ineligible during the first hour of the appointment and \$20 for those who complete the two hour appointment, regardless of eligibility or interest in continuing with the study.

Videotaped drinking session:

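### Does the lack of an alcohol use disorder item in the social-drinker definition undermine the social-versus-heavy comparison?

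*Combined protocol and SAP*

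**What the plan says.** Section 6, Screening phase, item a (Drinking behaviors) opens: "Past 30-day drinking behaviors and DSM-5 criteria for alcohol use disorder will be used as the basis for distinguishing social and heavy drinkers".

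- **Social drinkers** have two numbered conditions: 1 to 5 standard drinks a week, and binge frequency. The second is worded "engage in infrequent binge drinking (i.e., 5 or fewer times per year, but allowing for 1 past interval of a maximum of" six months, with a "duration of up to twice weekly binge drinking". Neither condition mentions AUD.
- **Heavy drinkers** have three: at least 10 drinks a week; binges "1 to 5 times on average per week"; and that they "meet DSM-5 criteria for mild or moderate alcohol use disorder".
- **Unclear cases:** "Those who drink but who did not clearly fall into one of these two groups will be excluded from participation".

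The general exclusion criteria in Section 6 remove those who "currently meet the severe threshold for alcohol use disorder according to DSM-5 (i.e., 6 criteria or more"). A separate exclusion applies to those who "currently meet DSM-5 substance use disorder criteria at any level (i.e., 2 or more criteria) for any substance besides alcohol", so it does not reach alcohol.

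The list of instruments (In-Person Screening) provides a structured DSM-5 interview that records past or present alcohol and other substance use disorders, and also the AUDIT.

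**The concern.** The opening sentence names two bases for separating the groups, drinking behaviour and AUD criteria, and the second is then applied on one side only. A reader who expects symmetry would look for a condition that social drinkers have no AUD, and there is none. A light drinker with mild or moderate AUD meets both social conditions and no stated exclusion.

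The allowance for one past period of up to twice-weekly binges makes the case easier to imagine. That rate lies within the heavy group's own range of 1 to 5 a week, and no minimum time since the period ended is given.

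If such people were enrolled, the social group would not be free of AUD. The study's hypothesis concerns AUD (Abstract), and Aim 3 seeks indicators of it, so a reader might take the social-versus-heavy contrast for a contrast of AUD with no AUD when it is not quite that. Two screeners might also decide the same case differently.

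**Working it through.** **Inputs.** Group rules and exclusions: Section 6, as above. Sample size: Section 6, up to 40 participants, about 10 in each of four cells. The lower limit of 2 criteria for any AUD is taken from the any-level threshold stated for other substances.

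**1. The plan's own figure.** 4 cells × 10 = 40, which agrees. Each drinking group spans two cells, so about 2 × 10 = 20 social and 20 heavy drinkers.

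**2. The rules applied literally, by number of AUD criteria.**

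| AUD criteria | 4 drinks/week, 3 binges/year | 15 drinks/week, 2 binges/week |
|---|---|---|
| 0–1 | social | neither group |
| 2–5 | social | heavy |
| 6 or more | excluded | excluded |

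The literal reading in the concern is confirmed: social admits counts 0–5, heavy admits 2–5. The right-hand column also shows that AUD does help to separate the groups, because a person drinking at the heavy level without AUD is left out. The opening sentence is therefore not contradicted. It does not promise that AUD appears in both definitions.

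**3. Can anyone meet both definitions?** No. Weekly intake is 1–5 in one and at least 10 in the other. The unresolved case is social or excluded, never social or heavy.

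**4. How many people?** The documents give no figure. If k of the 20 social drinkers had AUD, the difference in AUD proportion between groups would be 100 − 5k percentage points: 100, 95, 90 and 80 for k = 0, 1, 2 and 4. If a share p of eligible social drinkers had AUD, the chance of at least one among 20 would be 1 − (1 − p)^20: 33% for p = 2%, 64% for 5%, 88% for 10% and 99% for 20%. Both k and p are assumptions; the spread shows only that the documents do not settle the matter.

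**5. Would excluding such people help to isolate AUD?** With k AUD-positive social drinkers and all 20 heavy drinkers AUD-positive, the correlation between AUD status and drinking group is φ = √((20 − k)/(20 + k)).

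- k = 1: √(19/21) = 0.95
- k = 2: √(18/22) = 0.90
- k = 4: √(16/24) = 0.82
- k = 0 (all excluded): 1.00

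Exclusion makes the overlap complete. The overlap comes from the heavy definition, which requires AUD, and is present however the social definition is worded.

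**6. Which analyses use the label?** Aim 2 compares groups defined by drinking status and depressed mood. Aim 3 is stated separately and is not tied to the group label. The smoking work it follows (Section 4) related model indicators to dependence scores person by person, and the interview and AUDIT supply the matching data here.

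**The case for a change.** The strongest opposing case is that an eligibility rule with two defensible readings should be settled, and that one line would do it. The person in question meets every written social condition, so the clause for unclear cases does not obviously apply. The authors wrote an any-level exclusion for other substances and left alcohol out. The exclusions for withdrawal history and treatment seeking remove some people with AUD but not all. The interview records AUD, yet no text applies the result to the social group.

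All of that is correct as a reading of the text, and one part stands: from the rule alone, a reader cannot tell whether the social group is free of AUD.

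The rest carries less weight. Read with the opening sentence, the clause for unclear cases gives a screener a natural ground for excluding a light drinker who has the AUD level required of the heavy group. The binge allowance (26 weeks × 2 = up to 52 binges) is not evidence of AUD, and no section links the two. The same paragraph has staff ask how far recent drinking resembles the past 12 months and lifetime, which bears on a recently ended binge period even though no cut-off is set. Finally, the two possible clarifications point in opposite directions. Barring AUD from the social group makes AUD and group inseparable; admitting it keeps a few people who partly break that overlap. Choosing between them is a design preference, not the correction of an error.

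**Conclusion.** No change follows. The text leaves one case unstated: the light drinker with 2 to 5 AUD criteria. It does not contradict itself, the groups are disjoint on weekly intake, and Aim 2 remains a valid comparison of social with heavy drinking whichever way the case is decided. Aim 3 is not planned by group label.

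The size is at most 5 percentage points of the social group per person, taking about 20 social drinkers. The number of such people, and any effect on the topography results, cannot be derived from the documents. Under either reading the group contrast should not be read as isolating AUD, because every heavy drinker has it by definition.

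This is a gap that analysts fill sensibly. AUD status is already collected on everyone, so a table by drinking group shows exactly what the social group contains. The conclusion rests on the structured interview being carried out as listed, and on the contrast being reported under the label the plan gives it, drinking status.

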The overall goal is to pilot test and establish a procedure for video-assisted alcohol topography and explore its utility as an indicator of alcohol use disorder. Our specific aims include the following: (1) characterize drinking behavioral patterns by converting videotaped drinking episodes into various drinking related parameters (e.g., sipping frequency, sipping intervals, sipping duration, rest duration, sipping amount); (2) compare drinking behavioral patterns across groups defined by drinking status (social vs. heavy drinkers) and mental health status (elevated vs. non-elevated depressed mood); and (3) use advanced nonlinear modeling to quantify the behavioral pattern and to derive potential indicators for alcohol use disorder.

6. Research plan

Overview

There are 4 phases to this study: 1) pre-screening by phone; 2) in-person screening appointment; 3) the first alcohol drinking session with videotaping; and 4) follow-up appointment for retest. The figure below gives a timeline of the steps involved in the study. Each alcohol drinking session including all testing will require 3-4 hours.

Participants

Recruitment: Participants will be recruited through recruiting flyers (Attached) posted on the UF campus and vicinity, along with ads posted on online classified sites such as Craigslist and newspapers. Prospective participants who see one of these

advertisements and are interested in the study will contact the study initially via telephone, text, or email message. Study staff will answer any questions and conduct a preliminary phone screen among those who would like to pursue study participation.

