Study staff will conduct a brief phone screen to determine whether the participant meet the general criteria to be included in the study. If the participant is eligible based on the phone screen, study staff will schedule an appointment for in-person screening.

Screening phase:

An in-person screening will be conducted to give information about the study and determine eligibility. The initial screening appointment will take about 2 hours. During this appointment, we will interview the participants about their drinking habits, cigarette use, mood, menstrual cycle if female, medical and mental health histories. Participants will also be engaged in a timeline followback interview to update their alcohol, cigarette smoking and electronic cigarette use. The alcohol drinking that is part of this study may not be safe for those who are also using cocaine, opiates, phencyclidine, amphetamines, methamphetamine, barbiturates, methadone or benzodiazepines. For this reason, individuals whose urine drug test indicates use of one of these drugs will be excluded. Also, participants who arrive with a positive breath alcohol reading no higher than 0.02% may be able to remain at the research office until their breath alcohol level declines to 0.00% and then continue with the appointment or reschedule the appointment one time. However, individuals who arrive at an appointment with a positive breath alcohol reading a second time will be excluded from the study and offered local referral options for treatment. Finally, women who are pregnant, nursing or sexually active with opposite sex partners without use of birth control will not be able to participate in the study.

As part of the screening procedure, participants will be asked to complete a web-based questionnaire that covers topics including drinking motives; current drinking behaviors; reasons for drinking; and physical activity level.

Information will also be gathered to categorize the participants into subgroups based on their drinking behaviors and depressive symptoms:

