General questions regarding other inclusion/exclusion criteria: Two questions will list the other inclusion and exclusion criteria respectively, and ask participants whether or not any of the criteria pertain to them.

In-Person Screening

Withdrawal symptoms: The 10-item Clinical Institute Withdrawal Assessment for Alcohol (Revised) (CIWA-AR)²² will be used to assess severity of current withdrawal syndromes.

Depression: Patient Health Questionnaire (PHQ-2 and PHQ-9)^{23,24} will be used for depression screening.

Medical and psychiatric history: A medical and psychiatric history will be taken from all participants, which will cover the following conditions: hypertension, diabetes, high cholesterol, cardiac abnormalities, pancreatitis, renal insufficiency, cancer, pulmonary disease, thyroid conditions, history of head injury or other neurological problems, stomach or intestinal disorders and liver disease. Participants will also be asked whether they have ever been diagnosed with a psychiatric condition or received treatment for such a condition. Participants will be asked to report all medications, including over the counter medications and those that they are currently taking, including psychotropic medications. The Structured Clinical Interview for DSM-5 (First et al., 2015) will be used to classify patients according to the presence or absence of past or present alcohol and other substance use disorders.

Self-reported alcohol consumption: The Timeline Followback Interview (TLFB) (Sobel & Sobel) will be administered at the in-person screening and updated at outset of each alcohol drinking session. Participants will be given a blank calendar including memory prompts (e.g., holidays), which covers the designated time interval (the prior 30 days at initial screening) and asked to reconstruct their drinking behavior, cigarette and electronic cigarette usage over that interval. The TLFB has good test-retest reliability and good validity for verifiable events.

Family history of problem drinking: Family history is measured with a subscale taken from the *Addiction Severity Index*.²⁶ Participants are asked to indicate whether or not four classes of relatives on both their mother's and father's side ever "had a significant problem with alcohol or drugs, one that either lead to treatment or should have led to treatment."

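### Does the mood grouping fail because the protocol does not say whether PHQ-2 negatives complete the PHQ-9?

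*Combined protocol and SAP*

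**What the plan says.** Section 5 (Specific Aims) makes mood one of the two factors compared in Aim 2: "mental health status (elevated vs. non-elevated depressed mood").

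Section 6, Screening phase, item b (Depression) gives three rules:

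- Reference group: "The non-elevated depressed mood group will be those who scored less than 3 on PHQ-2 (i.e., negative PHQ-2").
- Elevated group: those who "scored 3 or more on the PHQ-2 (i.e., positive PHQ-2) and 5 or more on the follow-up PHQ-9".
- Exclusion: "Those who scored 20 or more (i.e., severe depression) will be excluded from the study". This sentence names no instrument and no mood group.

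The general exclusion criteria in section 6 rule out people who "meet criteria for severe depression or have any serious psychological or medical history that contraindicates alcohol consumption", with no score or instrument attached. The list of instruments, under In-Person Screening, says: "Patient Health Questionnaire (PHQ-2 and PHQ-9)^{23,24} will be used for depression screening". It does not say who completes which form.

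Item a (Drinking behaviors) ends with a rule for people who fit neither drinking group: "Those who drink but who did not clearly fall into one of these two groups will be excluded from participation". Item b has no matching sentence for mood.

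**The concern.** The PHQ-9 enters the group rules only on the elevated side, and it is called a follow-up there. That reads naturally as a stepped procedure in which a negative PHQ-2 ends the depression assessment. On that reading three things seem to go wrong.

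1. The exclusion at 20 or more cannot operate in the reference group, although the general criteria exclude severe depression for everyone.
2. The reference group could hold people whose PHQ-9 total, had it been taken, would fall in the elevated group's range. With no PHQ-9 for them, a report could neither show the overlap nor tell a null mood result from weakly separated groups. The affect scale given after drinking measures current mood and is no substitute.
3. A positive PHQ-2 with a PHQ-9 below 5 fits neither mood group, and no disposition is stated.

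Mood is half of the 2×2 layout, and a screening score that is not collected cannot be recovered later, so the point deserves a check.

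**Working it through.** The plan states no figure on this point, so there is none to reproduce. The check has two parts: what the text supports, and how large the consequences could be.

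**Reading the text**

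- For a stepped PHQ-9: the word follow-up, and a PHQ-9 condition that appears in the elevated rule only.
- For a PHQ-9 given to all: the instrument list names both forms without condition. Where that list restricts a measure to a subset it says so, as with pregnancy tests and menstrual data for women. The exclusion at 20 is not tied to a mood group, and the general severe-depression exclusion covers everyone. Both exclusions work as written if all participants complete the form.

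Neither reading can be ruled out. This is an ambiguity, not a demonstrated omission.

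**Score ranges**

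Assumption, not in the documents: nine items scored 0–3, with the PHQ-2 as the first two. The PHQ-2 then runs 0–6 and the other seven items 0–21. Since 6 is less than 20, the exclusion score must be a PHQ-9 total.

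Points needed on the other seven items = target total − PHQ-2 score:

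| PHQ-2 score | to reach 5 | to reach 20 | maximum total |
|---|---|---|---|
| 0 | 5 | 20 | 21 |
| 1 | 4 | 19 | 22 |
| 2 | 3 | 18 | 23 |

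- PHQ-2 negatives can have totals of 0–23. The elevated group, after both cut-offs, spans 5–19. Overlap across that whole band is arithmetically possible and needs as few as 3 to 5 points on the other items.
- A total of 20 or more with a negative PHQ-2 needs 18 to 20 of 21 points, close to the maximum on every remaining item.
- Unassigned cases (PHQ-2 positive, total below 5) are the pairs (3, 3), (3, 4) and (4, 4), that is, at most 1 point on the other seven items.

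**What still screens everyone on the stepped reading**

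The general severe-depression exclusion applies to all. At the screening visit "we will interview the participants about their drinking habits, cigarette use, mood, menstrual cycle if female, medical and mental health histories". The list of instruments adds a psychiatric history and a suicidality interview with its own exclusion. None is described as giving a PHQ-9 total, but the general criterion does not ask for one.

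**Weight in the analysis**

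- Reference group: 2 cells × about 10 = about 20, so each person is 1/20 = 5% of it. This does not say how many people overlap, and nothing in the documents does.
- A supporting analysis on the continuous PHQ-9, adjusted for drinking group, at the maximum n = 40 with one covariate: SE(z) = 1/√(40 − 1 − 3) = 1/√36 = 0.167. The 95% half-width in z is 1.96 × 0.167 = 0.327, and tanh(0.327) = 0.316. A partial correlation near zero would be known to about ±0.32. Recruiting into groups by a PHQ-2 cut also makes the normal-theory approximation doubtful.

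**The case for a change.** The strongest case for acting is that clarification is cheap and the loss is permanent. If PHQ-2 negatives are not given the PHQ-9, then seven short items in a visit of about two hours would let the severe-depression score rule work in both mood groups and let the report describe how far the groups differ in symptom level. The abstract calls the contrast depressed versus non-depressed, and a reader may expect the reference group to have been checked on the fuller scale.

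Part of this stands. The protocol does not say who completes the PHQ-9 or what the severe-depression exclusion rests on in each mood group. It gives no disposition for a positive PHQ-2 with a PHQ-9 below 5. A sentence on each would be a harmless tidy-up, with the disposition left to the sponsor. If PHQ-9 scores exist for both groups, a table of them by group would be useful description.

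What does not stand is the step from silence to a flaw. The harm depends on taking the adverse reading of one word. The research plan and the aims set the contrast as elevated versus non-elevated mood and define it by the PHQ-2; they do not promise separation on PHQ-9 totals. Splitting both groups at the same PHQ-2 cut, with a confirmatory step on the positive side, is a legitimate two-step definition. Overlap on a second scale would limit interpretation, but it would not be an error in the comparison.

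**Conclusion.** No change to the plan is needed. This is missing operational detail that staff can be expected to settle sensibly. Followed as written, the protocol gives two groups cleanly separated on the PHQ-2, and the Aim 2 comparison, group definitions and target of up to 40 participants are the same whichever reading holds.

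The consequences are small or cannot be sized. A missed exclusion at 20 needs 18 to 20 of 21 points on the other items, and several other screens cover all participants. The unassigned case needs at most 1 point on those items. Dilution of the mood contrast is possible but cannot be estimated, and no bias in Aim 2 is shown. The continuous PHQ-9 analysis is optional; at about ±0.32 it would be imprecise, and it corrects no stated rule.

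The score-range figures rest on standard 0–3 item scoring with the PHQ-2 as the first two PHQ-9 items, which the documents do not state. The reading of the text and the conclusion that the planned comparison is unchanged do not depend on that assumption.
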